## **22 RECORD RETENTION**

Study documents should be retained for a minimum of 2 years after the last approval of a marketing application in an ICH region and until there are no pending or contemplated marketing applications in an ICH region, or until at least 2 years have elapsed since the formal discontinuation of clinical development of the Study Drug.

After completion of the study and analysis of the data, the essential documents (ICH GCP E6 R2, Chapter 8) will be stored in the Trial Master File in the Sponsor's archive for at least 25 years according to new European Union (EU) regulations. The essential documents will be stored in the Investigator Site File for the longest of the following periods: for 15 years or for the record retention period mandated by any federal, state, or local laws or regulations. The subjects' files (hospital charts, source documents, etc.) will be stored for the same period, or at least for the

maximum period allowed by institutional policies, if not otherwise agreed to by the Sponsor in writing.

Once the storage period has elapsed, the PI must contact the Sponsor (contacts are provided in the CTA). The PI is not allowed to destroy the study related documents without prior written authorization from the Sponsor. The Sponsor will inform the PI when such documents no longer need to be retained.

## **22.1 BIOLOGICAL SAMPLES**

Biological samples will be managed, processed and analyzed at the sites selected laboratories. The samples will only be used for TH testing, and these tests should be performed within 24-72 hours of collection. Samples should not be stored for an extended period of time at the laboratory.

## **23 REPORTING**

A clinical study report (CSR) will be prepared by the Sponsor (or designee) according to ICH guidelines.

## **24 PUBLICATION POLICY**

The data collected during the study will be the property of the Sponsor. The Sponsor is entitled to publish and/or present any results of this study at scientific meetings, and to submit these clinical trial data to regulatory authorities. The PI agrees to treat any unpublished information supplied by the Sponsor or designee as confidential and ensure that confidentiality is maintained by all involved clinical site personnel.

The publication of any data derived from this study will be the result of a bilateral agreement between the PI and the Sponsor. The Sponsor has the right to review any manuscript about the study, and associated revisions will be delivered within 60 days of receipt. Revision of posters, abstracts or any other similar publications will be performed within 15 days. For multicenter studies, the Sponsor requires that the PI (or designee) does not publish any partial data before publication of the whole data set. The publication will neither disclose the identity of subjects nor any intellectual property information.

## **25 RESPONSIBILITIES**

The PI is responsible for personally supervising study conduct at their clinical site to ensure compliance with the protocol, ancillary study processes, ICH GCP, the Declaration of Helsinki

and applicable regulatory requirements. By signing this protocol, the PI attests to their understanding of, and commitment to upholding this responsibility.

| 10.3 | SOFTWARE TO BE USED | 25 |
| 10.4 | CODING DICTIONARIES | 25 |
| 11 | REFERENCES..... | 26 |
| 12 | APPENDIX 1: LIST OF TABLES, LISTINGS AND FIGURES | 26 |
| 13 | APPENDIX 2: SHELL TABLES, LISTINGS AND FIGURES | 26 |
| 14 | APPENDIX 3: PARENTS' SATISFACTION QUESTIONNAIRE SCORES..... | 26 |

LIST OF ABBREVIATIONS

| Abb. | Notes |
|----------|---|
| AE | Adverse Event |
| ATC | Anatomical Therapeutic Chemical |
| BMI | Body Max Index |
| BW | Body Weight |
| CH | Congenital Hypothyroidism |
| CI | Confidence Intervals |
| COVID-19 | Coronavirus disease of 2019 |
| CareCAT | Caregiver administered Children's Acceptance Tool |
| FAS | Full Analysis Set |
| FT4 | Free Thyroxine |
| IWRS | Integrated Web Response System |
| LT4 | Levothyroxine |
| MedDRA | Medical Dictionary for Regulatory Activities |
| PPS | Per Protocol Set |
| PSQ | Parents' satisfaction questionnaire |
| PT | Preferred Term |
| PTAE | Pre-Treatment Adverse Event |
| SAE | Serious Adverse Events |
| SAF | Safety Analysis Set |
| SAS | Statistical Analysis System |
| SOC | System Organ Calss |
| T4 | Thyroxine |
| TEAE | Treatment-Emergent Adverse Event |
| TFTs | Thyroid Function Tests |
| TH | Thyroid Hormone |
| TSH | Thyroid Stimulating Hormone |
| TT4 | Total Thyroxine |
| WHO-DD | World Health Organization Drug Dictionary |

1 INTRODUCTION

This document outlines the statistical methods to be implemented in the analysis of the data of IBSA 20US-T414 Clinical Trial. The purpose of this plan is to provide general guidelines from which the analysis will proceed, containing a more technical and detailed elaboration of the principal features of the analysis described in the protocol. In case of deviations from this updated statistical analysis plan, explanations will be provided in the statistical report.

2 VERSION HISTORY

| Version Number | Summary/Reason for changes | Date Issued |
|------------------|--|-------------|
| Draft 0.1 | First draft | 13/08/2025 |
| Final 1.0 | First final version | 15/10/2025 |
| Draft 1.1 | Section 7.1: LT4 medications will be summarized by Anatomical Therapeutic Chemical (ATC) level 2 and preferred drug name, separately from the prior and concomitant medications. Section 9.3: The demographic data analysis will be repeated stratified on neonates and infants. Section 9.4: The variables newly diagnosed neonates vs infants already on LT4 therapy and center will be removed from the analysis of covariances models. Interactions between visit and treatment group will be added to estimate the treatment effect at each visit. The visits included in the Parent Satisfaction Questionnaire analysis of covariance are specified. LT4 dose/kg, TSH and FT4 levels at each visit will be compared between treatment groups by Wilcoxon Mann-Whitney test. These comparisons will be repeated stratified on neonates and infants. | 09/03/2026 |

| | | |
|------------------|---|------------|
| | 
TSH values above 4.5 mU/L and FT4 values below the middle of the laboratory normal range will be analyzed also aggregate from Visit 2 to the last available visit.
 
Summary descriptive statistics will be provided for Parents' Satisfaction Questionnaire score and the results at each visit will be compared between treatment groups by Wilcoxon Mann-Whitney test. Descriptive statistics on aggregate CareCAT results will also be provided. During the first week, the third week, and the eighth week of administration CareCAT will be analyzed by day in each week and by week comparing the treatment groups by means Cochran-Mantel-Haenszel χ^2 test. Descriptive statistics on aggregate CareCAT results overall and by week will also be provided.
 | |
| Final 2.0 | 
Final version release.
 
Section 9.4.2: added growth pattern comparison between treatment groups by Wilcoxon Mann-Whitney test.
 | 24/03/2026 |

3 STUDY DESIGN

This is a multi-center, prospective, parallel-group, open-label, randomized clinical study in one hundred and twenty-six (126) subjects (neonates and infants diagnosed with congenital hypothyroidism (CH)).

Subjects will be randomized in a 2:1 ratio to Treatment (Tirosint®-SOL) or Control (levothyroxine sodium crushed tablets).

Newly diagnosed neonates will be randomly assigned to start therapy with Levothyroxine (LT4) at the initial dose recommended by the Standard of Care.

Infants already on LT4 therapy will continue at the same daily dose within the randomly assigned treatment group (dose adjustments are allowed, if needed based on laboratory parameters and clinical response).

Once enrolled, subjects will be treated and followed for 12 months (± 1.5 months), participating in 7-8 study visits, consisting of 6-7 in-clinic and 1-2 (or more if follow-up

visits are required) telemedicine visits. The total number of visits depends on the age at inclusion as reported in the Tables 1 Schedule of Evaluations and Table 2 Outline of Visit Schedule based on Age of the study protocol.

In-clinic visits are performed between 3-4 weeks after randomization, when the subject is 4, 6, and 9 months of age, and then every 3 months as required depending on the age at the inclusion. Telemedicine visits will be performed between 1-2 weeks after randomization, when the subject is 2 months of age, if applicable, and any time an additional follow-up is required for TSH and thyroxine (T4) monitoring.

For further details refer to Study Protocol n. 20US-T414 final version v2.0, Release date: September 7, 2023.

The study was originally planned to enroll a total number of 126 subjects (84 Treatment and 42 Control), expected between September 2021 and July 2022. Despite the extension of the study timeline, a protocol amendment and the efforts by the sites, the enrollment (screening) was closed on 31 March 2024 with a total of 31 randomized subjects, since reaching the enrollment target appeared no longer practicable within reasonable timeframe.

3.1 STUDY OBJECTIVES

Primary objectives

The main objectives of this study are to compare the use of Tirosint®-SOL and conventional treatment with crushed LT4 tablets in terms of:

- LT4 dose required to maintain TSH in target range;
- hormonal (TFTs) profile;
- parent/caregiver reports of satisfaction and ease of administration; and
- subject's acceptance of the treatment.

Secondary objectives

The secondary objective is to compare the study drug and the control treatment by assessing frequency of dose adjustments, and growth patterns (length, BW, head circumference).

Exploratory objectives

An exploratory objective is to compare the study drug and the control treatment in neonates only for the time required to normalize TSH and FT4 into their target ranges.

3.2 SAMPLE SIZE

Subjects were randomized in a 2:1 ratio to Treatment (Tirosint®-SOL) or Control (conventional therapy with LT4 crushed tablets). Considering a mean value of 6 mcg/kg/day of LT4 dose at 12 months of age and a standard deviation of 2 mcg/kg, a sample size of 102 neonates and infants (68 Treatment and 34 Control) will have 80% power to detect a difference of 20% in the LT4 dose between the groups using an independent t-test with a 0.050 two-tailed significance level. To account for a drop-out rate of maximum 20%, 126 neonates and infants will be enrolled in the study (84 Treatment and 42 Control) (Peroni 2013).

3.3 RANDOMISATION

This study was not blinded, all study staff was aware of the treatment assigned.

All eligible subjects were randomly assigned at Visit 1. Subject randomization was 2:1 (Treatment:Control) and stratified by site through an Integrated Web Response System (IWRS).

Randomization was stratified based on age:

- neonates newly diagnosed ≤ 28 days; and
- infants > 28 days already on therapy with LT4.

3.4 CHANGES FROM STUDY PROTOCOL

Section 19.2 Population for analysis:

The following subject populations were foreseen:

- Full Analysis Set (FAS): all randomized subjects;
- Per Protocol Set (PPS): all randomized subjects with no major protocol deviations; and
- Safety Analysis Set (SAF): all randomized subjects who received at least 1 dose of study medication.

Due to the premature termination of the study and the limited sample size the Per Protocol Set will not be considered for the final analysis.

Section 19.3.1 General Statistical Methods:

Due to the fast changing measurements in the specific population, in relation to growth, the last observation carried forward (LOCF) method will not be used to deal with missing data or in the case of early study discontinuation and missing data will not be replaced.

Section 19.3.2 Efficacy outcomes:

Due to the premature termination of the study and limited sample size all the efficacy analyses will be considered exploratory. LT4 dose/kg, laboratory parameters (TSH and FT4), “Parents’ Satisfaction Questionnaire” will be analyzed with a mixed model adjusted with Kenward-Roger method and considering as first choice the unstructured covariate matrix (other matrixes will be considered if there will be convergence problems). Variables newly diagnosed neonates vs infants already on LT4 therapy and center will not be considered in the models. Normal distribution for LT4 dose/kg, laboratory parameters (TSH and FT4), “Parents’ Satisfaction Questionnaire” will be tested with Shapiro Wilks, if data result not distributed as a normal distribution a log transformation will be applied. LT4 dose/kg, TSH and FT4 levels and Parents’ Satisfaction Questionnaire score at each visit will be compared between treatment groups by Wilcoxon Mann-Whitney test.

Section 19.3.3 Exploratory outcomes:

Time to TSH and FT4 normalization in the neonates will not be evaluated between the treatment groups due to the low number of neonates enrolled (3 randomized to Tirosint-SOL and only 1 to Control).

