### 13.1.2 DOSAGE AND ADMINISTRATION

Both products will be used and dosed according to the USPI and SOC.

The dose administered will be based on the subject's BW and age, and adjusted based on clinical response and laboratory parameters according to SOC and PI's judgement.

These procedures are informed by the main treatment guidelines, as well as in the USPI of Tirosint®-SOL and LT4 tablets ([Synthroid USPI](#), [Tirosint®-SOL USPI](#)), as described in **Section 11.3**.

**Further to these general principles, Investigators are required to follow the SOC in order to define the correct dose and treatment goal for each subject.**

Initial Dosing in newly diagnosed neonates:

- Replacement therapy with LT4 should be started as promptly as possible upon diagnosis of CH.
- **Inclusion in the study must not delay the start of LT4 treatment.**
- Initial neonate LT4 dose should be between 10-15 mcg/kg;
- The initial dose should take into account the severity of the disease; and
- The goal of therapy should be to normalize FT4 into the upper half of the reference range and TSH within the reference range (it is suggested, within the mid- to lower half of the reference range whenever appropriate).

Initial Dosing in infants already under LT4 therapy:

- Subjects will be switched directly from crushed LT4 tablets to Tirosint®-Sol or continue on crushed LT4 tablets, with **no treatment interruption**.
- Same dose used before screening should be maintained, if replacement is adequate at screening/inclusion; or
- Dose should be adjusted at inclusion, if needed based on laboratory parameters and clinical response.

Dosing throughout study in neonates and infants:

- Dose adjustments can be done whenever required throughout the study and will be defined based on the evaluation of T4 and TSH values and clinical response according to SOC; and
- Therapy should aim to maintain serum TSH concentration in the age specific laboratory reference range (it is suggested, to target the mid- to lower half of the reference range whenever appropriate) and serum T4 concentration in the upper half of the age specific laboratory reference range.

If dose fine tuning is required, which cannot be obtained with the available strengths, alternating two strengths over the course of the week may be allowed. All dosing schemes must be documented in the EDC.

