### 19.3.2 EFFICACY OUTCOMES

The LT4 dose/kg will be calculated based on the daily LT4 dose used in the time period preceding the visit and the body weight measured during the visit. When dosing schedules alternating strengths over the course of the week are used, the daily dose will be calculated as the average daily dose on a weekly basis. The LT4 dose/kg required to maintain TSH in target range will be

analyzed at 12 months of age visit (V8) and when the subject is 2, 4, 6, 9, 15, 18 and 21 months of age (V4, V5, V6, V7, V9, V10, V11) by means of analysis of covariance, including treatment group, newly diagnosed neonates vs infants already on LT4 therapy, age at inclusion and center as covariate.

Laboratory parameters (TSH and FT4) will be analysed at each time point by means of analysis of covariance, including basal value, treatment group, newly diagnosed neonates vs infants already on LT4 therapy, age at inclusion and center as covariate. If an adequate number of observations will be reached, the same analysis will be repeated for the TT4 parameter; otherwise the TT4 results will only be summarised by descriptive statistics.

The events of TSH values above 4.5 mU/L will be analyzed with a logistic model for each study visit with treatment group, newly diagnosed neonates vs infants already on LT4 therapy, age at inclusion and center as covariates. The laboratory result with a TSH value above 4.5 mU/L reported for the visit will be considered the analysis event.

The events of FT4 values below the middle of the laboratory normal range will be analyzed with a logistic model for each study visit with treatment group, newly diagnosed neonates vs infants already on LT4 therapy, age at inclusion and center as covariates. The laboratory result with a FT4 value below the middle of the laboratory normal range reported for the visit will be considered the analysis event.

Parent satisfaction assessed by “Parents’ Satisfaction Questionnaire” at each in-clinic visits (and during visit V1 only for infants that are already in therapy) will be analyzed by means of analysis of covariance, including treatment group, newly diagnosed neonates vs infants already on LT4 therapy, age at inclusion and center as covariate.

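### Site was a randomisation stratum, but the SAP removes it from the mixed models and does not restore it as a random effect; if sites differ, the dose/kg and satisfaction standard errors are modestly too large

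*SAP*

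**What the plan says.** Protocol 13.3 and SAP 3.3 describe a 2:1 allocation stratified by site and by age class (newly diagnosed neonates up to 28 days; older infants already on LT4). Protocol 19.3.2 carried both strata into the covariance analyses of dose/kg, TSH, FT4 and the satisfaction score, listing "newly diagnosed neonates vs infants already on LT4 therapy, age at inclusion and center as covariate".

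SAP 3.4, under its changes to that section, states: "Variables newly diagnosed neonates vs infants already on LT4 therapy and center will not be considered in the models". Accordingly, the mixed model for dose/kg (SAP 9.4.1) and the one for the questionnaire (9.4.2) contain treatment, age at randomisation and the visit-by-treatment interaction. The TSH and FT4 models add the basal value. Site appears in none of them, fixed or random. The same paragraph of 3.4 cites premature termination and the small sample, and SAP 9.4 calls all efficacy analyses exploratory. For dose/kg, TSH and FT4, the descriptive statistics and per-visit Wilcoxon tests are repeated within neonates and within infants. No such repeat is planned for the questionnaire.

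**The concern.** Balancing the arms within sites takes between-site differences out of the treatment contrast. A model that omits site leaves those differences in the residual variance, so it reports a larger standard error than the design produces. Confidence intervals are then too wide and the nominal 5% test rejects too seldom.

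Site is a plausible source of variation in dose/kg. Protocol 11.3.1 fixes no study-wide TSH or T4 target range and relies on the reference ranges of the sites' laboratories. Protocol 13.1.2 says that "Investigators are required to follow the SOC in order to define the correct dose and treatment goal for each subject". Protocol 13.1.1 leaves the choice of tablet product to the investigator. At stake is precision for the primary variable, in a trial that randomised 31 of 126 planned children.

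**Working it through.** **Inputs from the documents.** SAP 3.2: "Considering a mean value of 6 mcg/kg/day of LT4 dose at 12 months of age"; "a standard deviation of 2 mcg/kg"; "0.050 two-tailed significance level"; the planned sample "will have 80% power to detect a difference of 20% in the LT4 dose between the groups". The target difference is therefore 0.20 × 6 = 1.2 mcg/kg/day. SAP 3 gives 31 randomised; SAP 3.4 gives 4 neonates (3 and 1), hence 27 infants.

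**Assumptions, not in the documents.** Number of randomising sites (the synopsis allows up to 20; 5 to 20 tried); 2:1 permuted blocks of 3 or 6 within site × age class; share of dose/kg variance between sites, ρ, from 0 to 0.5; about 21 and 10 children per arm. All simulations use a single visit and total SD 2 and, unless noted, keep linear age in the model.

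**1. The plan's own figure.** A two-sided t-test with 68 and 34 children, difference 1.2 and SD 2 has 80.8% power; with 66 and 33 it has 79.6%. The 102 evaluable children are reproduced.

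**2. The trial as it stands.** SE = 2 × √(1/21 + 1/10) = 2 × √0.1476 = 0.77 mcg/kg/day. Then 1.2 / 0.77 = 1.56 standard errors, and power is about 33% before any site effect.

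**3. Ceiling on the excess.** With perfect balance in every site, the ratio of model SE to true SD is 1/√(1 − ρ): 1.05 at ρ = 0.1, 1.12 at 0.2, 1.20 at 0.3 and 1.41 at 0.5.

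**4. Why the ceiling is not reached.** From 5 to 20 sites means 31/5 = 6.2 down to 31/20 = 1.55 children per site, over 10 to 40 site × age-class cells. Many blocks stay incomplete. The simulated ratio of model SE to true SD, with site omitted and 5 to 20 sites, was:

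| ρ | model SE / true SD |
|---|---|
| 0 | 0.99-1.02 |
| 0.1 | 1.00-1.04 |
| 0.3 | 1.05-1.13 |
| 0.5 | 1.03-1.24 |

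Example with 10 sites, ρ = 0.3 and blocks of 3: the model without site reports 0.77 against a true SD of 0.68, and 0.77/0.68 = 1.13. A random site effect with ρ taken as known gives an SE of 0.67.

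**5. Error and power.** With 8 or 12 sites and site × age-class blocks of 3, the model without site has a true type I error of about 3-5% at ρ from 0.1 to 0.3. Power for 1.2 mcg/kg/day:

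| ρ | without site | random site intercept |
|---|---|---|
| 0.1 | 31-32% | 34-35% |
| 0.2 | 31-32% | 36-38% |
| 0.3 | 31-32% | 40-41% |

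At ρ = 0 there is no real gain. With crude degrees of freedom the random-intercept test has a null error of about 4-6%.

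A second set (12 or 20 sites, blocks of 3 or 6) gave 33-34%, 35-38% and 38-40% with the random intercept, against 30-33% without. Its null error was 4.9-6.4%; held to a true 5%, its power was 31-33%, 32-38% and 34-40%. The true SD of the estimate fell by only 1-2% at ρ = 0.2 and 2-3% at ρ = 0.3. Most of the gain is therefore restored calibration, not a better estimate.

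**6. The neonate/infant factor.** With age kept, 10 sites and no site effect, omitting it makes the SE 0-1% too large for stratum differences of 0 to 2 mcg/kg and about 4% for a difference of 4.

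**7. Center as a fixed effect, as in the protocol.** This is calibrated (coverage 94-96%) but costs degrees of freedom: 28 falls to about 15 with 20 sites. The mean 95% half-width then goes from 1.58-1.59 to 1.86-1.99 at ρ = 0.1 (worse) and from 1.56-1.57 to 1.39-1.48 at ρ = 0.5 (better).

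**The case against.** The strongest reply is that the between-site variance is unknown and may be small. The protocol gives all sites a common aim (TSH within, and FT4 in the upper half of, the age-specific reference range) and a common dose-by-age table. The change is openly declared, every efficacy analysis is exploratory, the error is on the safe side, and power stays near 40% or below either way. The first-choice unstructured covariance over V4 to V11 already has 8 × 9 / 2 = 36 parameters for 31 children, so another variance component may add to convergence trouble. All of this stands. It limits the weight of the point but does not give a reason to leave site out: a small sample argues against many fixed site effects, not against one variance parameter.

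A reader might also infer that both deleted strata do equal harm. For dose/kg they do not: 4 of 31 children are neonates and age stays in the model. For satisfaction there is some case for the factor, because it also marks prior experience with LT4, which a linear age term does not represent; no figure is available for that outcome.

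Finally, a reader might infer from the version history that the deletion was driven by results, since it is listed under a draft of March 2026, after a final SAP of October 2025, in an open-label trial. The documents do not show that anyone had seen comparative results, and the point does not rest on it.

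**Conclusion.** The point holds, at modest size. The SAP omits a randomisation stratum that the protocol had kept in the models. If sites differ, standard errors for dose/kg and satisfaction are conservative: for dose/kg about 0-4% too large at a 10% site share and 5-13% at 30%. Power for 1.2 mcg/kg/day is about 31-32%, against 34-41% with a random site intercept over site shares of 10-30%. These figures depend on the assumed sites, blocks and site share, and on a single-visit simulation; the repeated-measures model itself was not simulated. The satisfaction score has no stated SD, so for it only the direction is established.

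Two stronger readings are not supported. The omission does not create false positives, because the error runs the other way. Restoring site would not rescue the trial's power, because most of the gain is recovered calibration and the trial stays far below 80%.

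**What to change.** In SAP 9.4.1 and 9.4.2, add site as a random intercept to the dose/kg and questionnaire models and, for consistency, to the TSH and FT4 models, using the Kenward-Roger method already specified. State that the term is dropped only if its variance is estimated as zero.

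Reword the sentence in SAP 3.4; do not delete it, because it also declares the change for TSH and FT4. It should say that center enters as a random and not a fixed effect, and that neonate/infant is either kept as a factor with one degree of freedom or remains a declared omission.

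The per-visit Wilcoxon tests also ignore site, but replacing them by a van Elteren test stratified by neonate/infant is not needed. The neonate stratum has at most 3 against 1 children, and none at V9 to V11, because under Protocol Table 2 children randomised at 40 days or younger finish at V8.

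The cost is SAP wording and one random statement per model. The downside is one more variance parameter, which may require a simpler within-child covariance than unstructured; the SAP already allows other structures if convergence fails.

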### **19.3.4 SAFETY OUTCOMES**

Vital signs at each in-person visit will be analyzed descriptively within treatment groups.

Length, weight and head circumference will be analysed at each in-person visit by means of basal value, treatment group, newly diagnosed neonates vs infants already on LT4 therapy, age at inclusion and center as covariate.

The presence of signs and symptoms of hypo- and hyper-thyroidism at each planned visit will be compared between treatment groups by means of Chi test.

Number of subjects experiencing AEs and SAEs during the study will be calculated. Number of AEs and SAEs will also be calculated. Difference between treatment groups on subjects who experienced AEs and SAEs will be evaluated using a Chi test or a two-tailed Fisher's exact test as appropriate. Moreover adverse events will be described by MedDRA's System Organ Classes (SOCs) and Preferred Term (PT).

Similar summary tables will be provided for the number of AEs/SAEs at least possibly related to study treatment and for the number of AEs/SAEs leading to study discontinuation.

The number and percentage of subjects with AEs/SAEs will be summarized by their MedDRA preferred term within SOC.

Any subject reporting multiple episodes of the same AE/SAE (i.e. same preferred term) will be counted once.

Compliance will be calculated as the percentage of medication taken in relation to the recommended dose and the actual period of treatment (number of doses reported to be taken / number of doses envisaged x 100). Treatment Compliance will be described by means of descriptive statistics.

The number of subjects who need a dose re-adjustment during the long-term follow-up phase of the study will be compared between treatment groups by means of Chi test.

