10.1 Tolerability parameters

10.1.1 Adverse Events

The total number and percentage of subjects with at least one Adverse Event (AE), treatment-emergent Adverse Event, serious Adverse Event, drug-related Adverse Event, Adverse Event leading to treatment discontinuation and Adverse Event leading to death will be summarized by treatment group.

The following summary tables by treatment group will also be provided:

- Adverse Events by System Organ Class (SOC) and Preferred Term (PT);
- Serious Adverse Events by System Organ Class (SOC) and Preferred Term (PT);
- Treatment-Emergent Adverse Events by System Organ Class (SOC) and Preferred Term (PT);
- Drug related Treatment-Emergent Adverse Events by System Organ Class (SOC) and Preferred Term (PT);

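### SAP 10.1.1 no longer commits to the AE and SAE event counts or the between-arm comparison planned in protocol 19.3.4, and SAP 3.4 does not declare the change

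*SAP*

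**What the plan says.** Protocol 19.3.4 asks for more than a count of affected children. On events it says "Number of AEs and SAEs will also be calculated". On the arms it says "Difference between treatment groups on subjects who experienced AEs and SAEs will be evaluated using a" chi-squared test or a two-tailed Fisher's exact test, as appropriate. It also sets a rule for the subject-level tables: "Any subject reporting multiple episodes of the same AE/SAE (i.e. same preferred term) will be counted once".

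SAP 10.1.1 promises "The total number and percentage of subjects with at least one Adverse Event (AE), treatment-emergent Adverse Event, serious Adverse Event, drug-related Adverse Event", and further that "Adverse Event leading to treatment discontinuation and Adverse Event leading to death will be summarized by treatment group". It adds four SOC/PT tables by arm (AEs, SAEs, TEAEs, drug-related TEAEs) without saying whether they count children or events. It names no between-arm test and no event count. SAP Appendices 1 and 2 (table list and shells) are marked not applicable, so they do not settle the counting unit.

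SAP 3.4 declares changes to protocol 19.2, 19.3.1, 19.3.2 and 19.3.3. Its final sentence, for 19.3.3, begins "Time to TSH and FT4 normalization in the neonates will not be evaluated between the treatment groups due to the low number of neonates enrolled". There is no entry for 19.3.4, and the version history in SAP section 2 does not mention AEs. SAP section 1 promises explanations for departures from the SAP, which would not pick up a departure of the SAP from the protocol.

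**The concern.** Two planned safety outputs are missing from the SAP, and a reader who relies on its list of changes would not know.

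The sample size does not explain the omission as written. SAP 3.4 and 9.4 give low numbers as the reason for treating efficacy as exploratory and say nothing about safety. In the same 31 children, SAP 9.4.2 keeps between-arm tests on TSH above 4.5 mU/L, FT4 below mid-range, dose re-adjustment, and signs and symptoms of hypo- or hyperthyroidism.

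The event counts are the more useful of the two. A percentage of children with at least one AE gives the same weight to a child with one event and a child with six. It also takes no account of how long each child was observed. With both commitments gone, nothing in the SAP obliges the report to show how many adverse events occurred in each arm, or over how much observation time.

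**Working it through.** **1. Protocol against SAP**

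| Protocol 19.3.4 | SAP 10.1.1 | SAP 3.4 |
|---|---|---|
| Children with AEs and SAEs | kept, by arm | no entry needed |
| Number of AE and SAE events | not committed | no entry |
| Chi-squared or Fisher test on children with AEs and SAEs | not named | no entry |

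**2. The plan's own figures.** The only power calculation concerns LT4 dose: difference 0.20 × 6 = 1.2, SD 2, 68 v 34. It reproduces (noncentral t power 80.8%, stated 80%) but has no bearing on AEs. No expected or observed AE rate is given. The arm sizes are not stated either; 31 × 2/3 = 20.7, so 21 v 10 is assumed below.

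**3. Follow-up by entry age** (protocol Table 2, last visit with its ±21-day window)

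- Shortest: 455 − 138 − 21 = 296 days (last visit V9), and likewise 545 − 228 − 21 = 296 days (V10).
- Longest: 455 − 41 + 21 = 435 days (V9).
- Ratio of extremes: 435/296 = 1.47.

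This is the range between individual children who complete the study, not between arms.

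**4. How informative is the percentage?** All rates here are assumptions, with one year of follow-up. P(at least one AE) is 1 − exp(−λ) if counts are Poisson, and 1 − 1/(1 + λ) if children differ strongly in AE rate (negative binomial, k = 1). Power is used only as a yardstick of information, for a doubled rate in the solution arm, 21 v 10. Fisher power is by enumeration; count-based power is from 4,000 simulations. The count test is a conditional exact test under Poisson and a Wilcoxon test on counts per child under k = 1.

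| Control AEs per child-year | Controls with ≥1 AE, Poisson | Fisher | Count test | Controls with ≥1 AE, k = 1 | Fisher | Count test |
|---|---|---|---|---|---|---|
| 0.5 | 39% | 16% | 25% | 33% | 8% | 14% |
| 1 | 63% | 24% | 51% | 50% | 9.5% | 18% |
| 2 | 86% | 11% | 84% | 67% | 9% | 23% |
| 3 | 95% | 1% | 96% | 75% | 8% | 25% |
| 4 | 98% | 0.1% | 99% | 80% | 6.5% | 25% |

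For a rate ratio of 1.5 the count test falls to 10–62% (Poisson) and 6–11% (k = 1).

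An overdispersion-corrected rate model with follow-up of 296–435 days gives the same picture:

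- Rate ratio 2, 2–4 AEs per child-year, dispersion 0–0.5: 34–98%.
- Same rates, rate ratio 1.5: about 13–55%.
- Rate ratio 2, same rates, dispersion 1: about 18–22%.
- Rate ratio 2, 0.5 AEs per child-year: no better than Fisher (5–15% v 8–17%).

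**5. What the percentages can still show.** With 21/21 in one arm, Fisher p is 0.323 against 9/10, 0.097 against 8/10 and 0.027 against 7/10. Away from the ceiling, a 30-point difference has only 26–32% power. The sample size therefore limits the comparison whether or not there is a ceiling.

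**6. An empty SAE cell.** The exact two-sided 95% upper limit for zero events is 1 − 0.025^(1/n): 1 − 0.025^(1/10) = 31% for 10 controls, and 1 − 0.025^(1/21) = 16% for 21 children on solution.

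**7. Collection windows.** Under protocol 17.5, non-serious AEs are recorded to end of study or discontinuation, and SAEs to 25 days later. That adds 25/365 = 0.07 child-years per child to the SAE denominator.

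**The case against.** The strongest reply is that this is a documentation gap with little analytic cost. Much of it stands.

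- The missing test used the same per-child yes/no measure as the percentages. In most scenarios above its power is below 20%, so restoring it would add almost nothing.
- A reader might infer that all that remains is one near-ceiling percentage. The documents do not support that. Rows for SAEs, drug-related AEs, discontinuations and deaths remain by arm, as do four SOC/PT tables, and nothing suggests these are near a ceiling. The SOC/PT tables might even include event counts, although the SAP does not commit to them.
- A ceiling on the overall AE percentage is itself an assumption. Protocol 15.1.1 keeps abnormal thyroid laboratory results out of AE reporting altogether, and 15.2.3 admits hypo- and hyperthyroid signs only when clinically significant. Either rule could hold the AE rate down.
- Nor can it be said that the percentages cannot show a difference: 21/21 against 7/10 would be visible.
- The advantage of counts is large only with frequent events, a doubled rate and mild variation between children.
- SAP 9.1 says that 95% intervals will be calculated, without restricting this to efficacy. It does not say for which safety quantity or by what method.
- Follow-up differences depend on entry age, which randomisation partly balances through the neonate/infant strata.

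The reply leaves two facts untouched: planned event counts are no longer promised, and the list of changes does not say so.

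**Conclusion.** The point holds as an undeclared change with a modest loss of information. Protocol 19.3.4 plans AE and SAE event counts and a between-arm comparison; SAP 10.1.1 commits to neither and SAP 3.4 is silent. This rests on the text alone.

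The size of the loss rests on assumptions: 21 v 10 children and 0.5 to 4 AEs per child-year. If AEs are frequent, the percentage with at least one AE has little ability to show a difference in burden, and counts with observation time say more. At low rates, or with strong variation between children, the gain is small. In every case the 31 children are the main limit, so event counts should not be presented as giving this trial an adequately powered safety comparison.

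The trial was open-label and the SAP was finalised after enrolment closed, so a reader might infer that the comparison was removed because of what the data showed. The documents give no reason for the omission and no evidence for that inference. What is missing is the explanation.

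**What to change.** In SAP 10.1.1:

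- Report by arm, for TEAEs and separately for SAEs, the number of events, child-years of observation and rate per child-year. State that every episode counts as an event here; the protocol's count-once rule applies to the subject-level tables.
- Match each denominator to its collection window: to end of study or discontinuation for TEAEs, and to 25 days later for SAEs. State whether pre-treatment SAEs are included.
- Give the exact 95% interval for the proportion of children with an SAE in each arm.
- State whether the SOC/PT tables count children, events or both.
- Present all of this descriptively, without significance claims. A rate ratio with an overdispersion-corrected interval is optional and should not be justified by test power.

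In SAP 3.4, add an entry for protocol 19.3.4 saying that the AE/SAE test is dropped and why. The same entry can record two other changes to 19.3.4 not listed there: growth is compared by Wilcoxon tests instead of covariate-adjusted models, and signs and symptoms are compared once instead of at each planned visit.

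Cost: one extra table and a few sentences. AE recording and the date of last dose are already part of the plan, but the case report form is not in the documents, so the availability of each date should be confirmed. The intervals will be wide and will look less reassuring than bare percentages.
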